Study Protocol Document

Research Official A Prospective Study on Safety and Efficacy

Title: of Stenting for Chronic Middle Cerebral

Artery Occlusion With Limb Dysfunction

Filedate: March 1, 2021

A prospective study on the safety and efficacy of stent placement in the treatment of chronic middle cerebral artery occlusion with limb dysfunction

I. Research Background

The middle cerebral artery (MCA) is one of the main blood vessels that supply most areas of the cerebral cortex. When chronic occlusion occurs in MCA, it seriously affects blood flow to multiple important areas of the brain, including areas that control speech, sensation, and motor function. Therefore, MCA occlusion is often associated with severe neurological deficits such as hemiplegia, speech impairment, and cognitive impairment. Chronic MCA occlusion is usually caused by intracranial atherosclerosis, a procession in which the arterial wall gradually accumulates fat and calcium, leading to narrowing of the vessel. When blood vessels narrow to a certain extent, blood flow is reduced to a level that is insufficient to meet the needs of brain tissue, which can result in ischemic brain injury. Studies have shown that hypertension and diabetes are the main risk factors for intracranial stenosis and chronic MCA occlusion. These conditions increase the risk of MCA occlusion by accelerating the process of atherosclerosis, increasing the thickness and stiffness of blood vessel walls. In addition, smoking is another important controllable risk factor, which increases the risk of atherosclerosis by damaging vascular endothelial function and promoting inflammatory reaction.

Although there has been sufficient research on acute MCA occlusion, including vascular recanalization protocols during the acute phase, such as thrombolysis and mechanical thrombectomy, there is limited research on chronic MCA occlusion. Due to the long-term and complex nature of the disease course, the treatment strategies and prognosis evaluation for patients in the chronic phase are not yet clear. In addition, for patients who have not received timely or ineffective acute treatment, how to improve their long-term prognosis through interventional treatment is a major challenge in current research.

Previous case reports and retrospective studies have shown that even after years of MCA

occlusion, vascular reconstruction surgery can still successfully restore blood flow and achieve good therapeutic effects. However, currently, the vascular reconstruction treatment for chronic MCA occlusion is mainly limited to case reports, and there is a lack of systematic prospective studies to verify the safety and effectiveness of these treatments.

Given the above background, this study aims to fill this research gap by systematically evaluating the efficacy and safety of stent placement in patients with chronic MCA occlusion through prospective clinical trials, in order to provide more scientific and standardized treatment guidance for such patients.

II. Research Purpose

The aim of this study is to evaluate the safety and effectiveness of stent placement in patients with chronic MCA occlusion, and to explore its impact on blood flow recovery, reduction of reocclusion rate, and improvement of neurological function recovery.

III. Research Methodology

1. Research Design

This study adopts a prospective, single center, observational clinical trial design. By setting up a stent group and a control group, the therapeutic effects of the two groups of patients were compared to evaluate the safety and effectiveness of stent placement in patients with chronic middle cerebral artery (MCA) occlusion. This study has been approved by the Clinical Ethics Committee of Huishou Central People's Hospital in terms of human research ethics, and strictly adheres to relevant ethical standards and guiding principles.

2. Study Participants

Selection Criteria:

- 1) Age 18 and above, male and female unlimited.
- 2) Chronic occlusion of MCAconfirmed by magnetic resonance imaging (MRI) or computed tomography (CT), lasting more than 3 months.
- Neurological deficits caused by MCA occlusion, such as hemiplegia, speech disorders, etc.
- 4) Have not received MCA stent revascularization treatment in the past three months.

Exclusion Criteria:

- 1) Acute stroke occurred within the past three months.
- Severe heart disease, liver and kidney dysfunction, cerebral hemorrhage, active bleeding, or coagulation dysfunction.
- 3) Allergy to contrast agents.
- 4) Serious mental illness or inability to comply with research requirements.
- 5) Pregnant or lactating women.
- 6) MCA occlusion was found without any symptoms.
- 7) Participated in other clinical trials within the past six months.

3. Research Process

Participants first undergo detailed screening to ensure that they meet the inclusion and exclusion

criteria. Afterwards, all patients or their legal representatives are required to sign an informed consent form. Subsequently, patients will be randomly assigned to either the stent group or the control group. The control group received aspirin treatment, while the stent group underwent stent placement surgery on the basis of aspirin treatment.

4. Stenting Method

The patient underwent whole brain angiography in the intervention room, and the Seldinger technique was successfully used to puncture the right femoral artery and insert a 5F sheath. Insert the 5F pigtail catheter and vertebral artery catheter sequentially through the sheath tube for angiography to identify occlusion of left or right MCA. Next, the MCA stent is inserted, and the 0.014-inch microwire and microcatheter are successfully navigated to the left or right MCA occlusion site through the catheter. Then, the microcatheter is exchanged, and an appropriately sized intracranial self expanding stent is placed and released. After surgery, the femoral artery puncture site was sutured using a vascular closure device.

IV. Statistical Analysis

Use R software (version 4.1.2) for statistical processing. Classified data is presented in frequency and percentage, while continuous data is represented in mean \pm standard deviation or median and interquartile range. Inter group comparisons were conducted using methods such as independent sample t-test, Mann Whitney U test, chi square test, or Fisher's exact test.

V. Research Plan

Preparation phase (March 2021- April 2021): Obtain ethical approval, prepare and review all research documents (including informed consent forms and research protocols), and

establish a data management system.

Recruitment stage (May2021 November 2021): Identify eligible patients through the neurology and interventional radiology departments of collaborating hospitals, screen for inclusion and exclusion criteria, and obtain informed consent from patients.

Treatment stage (December 2021- January 2022): Arrange stent placement surgery or start standard drug treatment for eligible patients.

Follow up stage (February 2022- February 2023): Regular follow-up will beconducted on all participants to evaluate treatment outcomes, including blood flow recovery, reocclusion rate, and neurological function recovery. The follow-up time points is 3 months after surgery.

Data analysis stage (March 2023 September 2023): Collect all data, conduct statistical analysis, compare the differences between the two groups, and write a research report.

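### Assignment follows consent with no date, concealment or strata, although recruitment closes before treatment starts: the arm may be known long beforehand, and starting severity is uncontrolled.

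*Combined protocol and SAP*

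**What the plan says.** Section III.3 (Research Process) sets the order as screening, then consent ("all patients or their legal representatives are required to sign an informed consent form"), then assignment: "Subsequently, patients will be randomly assigned to either the stent group or the control group". It gives no date for the assignment and no sequence method, ratio, blocking, stratification or concealment.

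Section V (Research Plan) gives the calendar. The recruitment stage runs from May to November 2021. Its listed tasks are to identify patients, "screen for inclusion and exclusion criteria, and obtain informed consent from patients"; assignment is not among them. The next entry is "Treatment stage (December 2021- January 2022): Arrange stent placement surgery or start standard drug treatment for eligible patients". It does not mention assignment either. Follow-up is timed from the operation: "The follow-up time points is 3 months after surgery".

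On starting severity, the selection criteria in section III.2 admit "Neurological deficits caused by MCA occlusion, such as hemiplegia, speech disorders, etc" and name no scale or cut-off. Section IV lists only unadjusted two-group tests. Recovery of neurological function is among the outcomes in sections II and V.

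**The concern.** The calendar recruits the whole cohort first and treats it afterwards, so every patient waits between consent and treatment. One arm has an operation and the other has aspirin alone, and no blinding is described, so an assignment made at consent would be known throughout that wait. A patient given aspirin might withdraw or arrange stenting elsewhere; a patient given the stent might change their mind. Losses of this kind depend on the arm. They can bias the comparison even if everyone who starts treatment is followed completely, and re-checking eligibility in December would not bring those patients back.

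Separately, patients with any symptomatic deficit can enter, the design does not balance the arms on severity, and the analysis does not adjust for it. In a small trial with neurological recovery as an outcome, a chance difference in starting severity could blur the result or make it hard to interpret.

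**Working it through.** The documents give no sample size, allocation ratio or waiting time, so there is no figure of the plan's own to reproduce.

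**Length of known allocation.** Section V gives months only. I assume the outer days: consent 1 May to 30 November 2021, treatment 1 December 2021 to 31 January 2022.

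- Longest gap, 1 May to 31 January: 214 days to 1 December + 61 = 275 days.
- Shortest gap, 30 November to 1 December: 1 day.
- A patient who consents on 1 May waits at least 214 days.
- Mean gap if both sets of dates are spread evenly: the middle of consent is day 106.5 after 1 May and the middle of treatment is day 244.5, so 244.5 − 106.5 = 138 days.

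These are gaps from consent to treatment. They become periods of known allocation only if assignment is made and disclosed at consent.

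**Known allocation after the fix.** If the whole list is released on 1 December, the longest period is 1 December to 31 January = 61 days. Release patient by patient shortens it further.

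**Chance imbalance in severity.** Assumptions: total N, equal arms, and a normally distributed severity score with SD 1. Without strata, the standard error of the difference in mean severity is 2/√N, and P(|difference| > 0.5 SD) = 2[1 − Φ(0.5/(2/√N))]. For N = 40: 2/√40 = 0.316; 0.5/0.316 = 1.58; P = 0.114.

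The stratified column comes from a simulation with 20,000 runs per N of a 1:1 draw within two strata split at the median score.

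| Assumed total N | 2/√N | No strata | Stratified at the median |
|---|---|---|---|
| 20 | 0.447 | 26% | 7% |
| 40 | 0.316 | 11% | 1.0% |
| 60 | 0.258 | 5.3% | 0.2% |
| 100 | 0.200 | 1.2% | under 0.1% |

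Stratifying leaves the SD of the chance difference at 0.60 to 0.62 of its unstratified value. That agrees with theory: the variance within half of a normal distribution is 1 − 2/π = 0.363, and √0.363 = 0.60. The difference is reduced but not removed, because severity still varies within each stratum.

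**The case against.** The strongest objection is that the timing problem rests on silence. Assignment is not listed in the recruitment stage, and the treatment stage is the first with arm-specific actions ("Arrange stent placement surgery or start standard drug treatment for eligible patients"). Assignment in December fits the text as well as assignment at consent. This stands. A reader might infer that patients will know their arm for 275 days, but the documents do not say so. That figure needs assignment at consent, consent on the first possible day and treatment on the last. What remains is that the plan permits this and does nothing to prevent it.

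A reader might also infer simple, one-at-a-time randomisation, with enrolling staff guessing the next arm from earlier ones. The text says only that assignment is random. Under simple randomisation past assignments carry no information about the next, so that mechanism is not supported.

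The chance-imbalance argument has limits too. Randomisation tests already allow for chance imbalance, so it is not bias. The percentages depend on an assumed N, and the risk is small by N = 100. Unequal arm sizes matter even less: a 60:40 split keeps 4 × 0.6 × 0.4 = 0.96 of the information.

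Section V does plan follow-up of every participant, which would help if those lost before treatment were kept in. It does not prevent withdrawal, and a time point counted from surgery does not cover what happens before it.

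Finally, a reader might expect one late stratified draw to remove both problems. It does not: up to 61 days of known allocation remain if the list is released all at once, and only the stratified factor is balanced, at the chosen cut.

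**Conclusion.** The point holds in a limited form and should be acted on. The plan permits open allocation to be known well before treatment, for up to 275 days in the worst case, and neither design nor analysis controls starting severity. The worst case assumes assignment at consent and the outer calendar dates. The resulting arm-dependent loss cannot be sized from the documents.

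The imbalance risk is about 26%, 11% and 5% at assumed totals of 20, 40 and 60 and about 1% at 100, for a difference above 0.5 SD with equal arms and a normal score. It costs precision and comparability and does not invalidate the tests.

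The remedy is more than filling in a missing detail. Because the cohort is complete before treatment begins, one late, concealed, stratified draw is available within the existing timetable.

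**What to change.** - **Sections III.3 and V:** state that assignment is held until recruitment has closed. The list is then drawn once, 1:1 within two strata (above or below the median of a named baseline deficit score recorded before the draw), by someone who does not enrol patients. Keep the list concealed and release each assignment as close as practicable to that patient's scheduled treatment.
- **Section IV:** include the baseline score or the stratum in the comparison of neurological outcome.
- **Section III.1:** reconcile the observational label with the random assignment in III.3; the points above apply only if the study is randomised.
- **If the calendar changes so that recruitment and treatment overlap:** a single draw no longer works. Use concealed, stratified blocks of varying size, with each patient assigned on the day treatment is scheduled.

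The cost is wording in these sections, one script in R (already the named software), and the choice and recording of a baseline deficit scale, which the plan does not yet name. No extra staff are needed, provided that someone outside enrolment can draw and hold the list. The downside is that patients learn their arm later.

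### Patients randomised to stenting whose procedure fails or is never done have no defined assessment time and no guarantee of staying in the stent arm

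*Combined protocol and SAP*

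**What the plan says.** Section III.3 forms the groups by chance: "Subsequently, patients will be randomly assigned to either the stent group or the control group". Section III.1 labels the study differently: "This study adopts a prospective, single center, observational clinical trial design".

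Section III.3 then describes the stent arm by what it received: "the stent group underwent stent placement surgery on the basis of aspirin treatment". Section III.4 describes the procedure along its successful path only. It says that "the 0.014-inch microwire and microcatheter are successfully navigated to the left or right MCA occlusion site through the catheter", and then that "an appropriately sized intracranial self expanding stent is placed and released". Failed, aborted or unperformed procedures and crossover are not mentioned.

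Section V promises that "Regular follow-up will beconducted on all participants to evaluate treatment outcomes", and lists blood flow recovery, reocclusion rate and neurological recovery as the outcomes. It gives one time point: "The follow-up time points is 3 months after surgery". The data analysis stage in the same section compares the two groups. Section IV lists tests but names no analysis set and gives no rule for patients who did not receive their assigned treatment.

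**The concern.** Randomisation protects the comparison only if patients are counted where they were assigned. Here the arm is worded by treatment received, the design label is observational, and the assessment clock starts at surgery. An analyst following this text has no instruction for a patient assigned to stenting who ends without a stent. That patient could be kept in the arm, left out for want of a dated visit, or counted with the controls because aspirin was the only treatment actually received.

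Only the stent arm has a procedure that can fail, so loss or misplacement by this route is one-sided. If the patients concerned have harder lesions or procedural complications, the remaining stent arm looks better than the arm that was randomised, and complications of failed attempts may drop out of its safety result.

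Two related gaps come from the same wording. Controls have no surgery and hence no stated assessment time. Reocclusion has meaning only in a vessel that was first reopened, so a reocclusion rate in controls who were never recanalised is not a meaningful comparator.

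**Working it through.** The documents state no sample size, power, significance level, outcome rate or procedural failure rate, so there is no figure of the plan to reproduce. The check has two parts.

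**1. Does the text settle where and when each patient is counted?**

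| Patient | Arm stated for analysis | Assessment time stated |
|---|---|---|
| Assigned to stenting, stent placed | Stent | Three months from surgery |
| Assigned to stenting, procedure failed or aborted | Not stated | Unclear whether the attempt counts as surgery |
| Assigned to stenting, procedure never done | Not stated | None |
| Assigned to control | Control | None |

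Only the first row is fully defined.

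**2. What could the gap do? (illustration only)**

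Assumptions, none from the documents: no true stent effect; good-outcome rate p = 0.40 in both arms as randomised; 50 patients per arm; failure share f; good-outcome rate q among failures; pooled two-proportion z-test, normal approximation, two-sided 5% level.

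- Rate among successfully stented patients: s = (p − f·q)/(1 − f).
- Bias if failures are dropped: s − p.
- Control rate if failures are moved there: c = (p + f·q)/(1 + f). Bias: s − c.

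Worked case, f = 0.20 and q = 0.20:

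- s = (0.40 − 0.04)/0.80 = 0.450, so dropping gives +5.0 points.
- c = (0.40 + 0.04)/1.20 = 0.367, so moving gives 0.450 − 0.367 = +8.3 points.

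| f | q | Dropped: bias (type I error) | Moved to control: bias (type I error) |
|---|---|---|---|
| 10% | 0.30 | +1.1 points (5.1%) | +2.0 points (5.5%) |
| 20% | 0.20 | +5.0 points (7.7%) | +8.3 points (13.3%) |
| 30% | 0.20 | +8.6 points (12.3%) | +13.2 points (25.1%) |
| 40% | 0.20 | +13.3 points (21.2%) | +19.0 points (43.0%) |
| 10% to 40% | 0.40 | 0 (5.0%) | 0 (5.0%) |
| 10% | 0.50 | −1.1 points (5.1%) | −2.0 points (5.5%) |
| 40% | 0.50 | −6.7 points (8.9%) | −9.5 points (13.9%) |

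With failures kept in the assigned arm, the expected difference is 0 and the type I error 5% for every f and q.

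A second set of assumptions fixes the rate among successes, pS, at 0.40 or 0.50, and the rate among failures at 0.20, with f from 0.1 to 0.3. The arm rate as randomised is (1 − f)·pS + f·0.20.

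- Lowest case (f = 0.1, pS = 0.40): arm rate 0.38; dropped 0.40 − 0.38 = 2.0 points; moved 0.40 − (0.38 + 0.02)/1.1 = 3.6 points.
- Highest case (f = 0.3, pS = 0.50): arm rate 0.41; dropped 0.50 − 0.41 = 9.0 points; moved 0.50 − (0.41 + 0.06)/1.3 = 13.8 points.

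**The case against.** A reader might infer that the protocol defines the stent group as the technically successful patients and so builds in a bias toward stenting. The documents do not support that. Groups are formed by random assignment before any procedure, Section III.4 describes technique and defines no analysis group, and its sentence on navigation speaks of reaching the occlusion, not of crossing it. Section V promises follow-up of all participants and describes the treatment stage as intended care. Nothing in the text excludes, replaces or reclassifies anyone.

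A reader might also infer that patients whose angiogram shows no occlusion will be removed from the stent arm alone. Catheter angiography, used "for angiography to identify occlusion of left or right MCA", is indeed described only within the stenting procedure. But entry already requires occlusion confirmed by MRI or CT, the phrase can equally mean locating the lesion, and no consequence of a negative angiogram is stated.

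Finally, bias toward stenting is conditional. It needs failures to be dropped or moved, and to do worse than average.

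All of this stands, and it makes the flaw an omission and not a stated exclusion. It does not close the gap. Following every participant does not say in which arm a failed case is counted, and the one stated time point does not exist for a patient who was not operated on.

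**Conclusion.** The concern holds as a gap in the plan that should be closed. The text leaves failed, aborted and unperformed stenting without an assigned place in the analysis or a clear assessment time, leaves controls without a time anchor, and lists a reocclusion outcome that cannot be compared meaningfully with controls who were never recanalised. The conflict between the observational label and random assignment adds to the doubt over whether groups will be compared as assigned or as treated.

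Neither the size nor the direction of any bias can be computed from the documents. The illustrations range from −9.5 to +19.0 percentage points and rest wholly on assumed rates and an assumed 50 per arm. A bias in favour of stenting is plausible if failures have the worse prognosis, but the documents give no data on that.

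**What to change.** - In Sections III.1, III.3 and IV, reconcile the observational label with random assignment, and state that the main efficacy and safety comparisons include every randomised patient in the assigned arm, whatever the angiogram or procedure shows. Complications of failed attempts then count in the stent arm.
- Measure outcomes, blood flow included, in failed and unperformed cases as in everyone else. Scoring them by rule as no recovery is unnecessary, because these patients can be measured, and it would treat the arms differently.
- Use one time anchor for both arms that does not depend on completed surgery, and reconcile it with Section V. Recruitment runs from May to November 2021, treatment from December 2021 to January 2022, and randomisation is undated. If it took place at enrolment, a three-month visit for a May 2021 patient would fall in August 2021, before treatment. Timing from randomisation works only if randomisation takes place at the start of the treatment stage.
- Report technical success with all patients assigned to stenting as the denominator. Report reocclusion descriptively among recanalised patients only, with the number of failures beside it.

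The cost is mainly protocol wording, plus settling when randomisation takes place. The downside is a possibly more conservative efficacy estimate.

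### The plan has no rule for patients who die, withdraw or go unassessed before 3 months, so by default they leave the comparison, and such loss may differ by arm

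*Combined protocol and SAP*

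**What the plan says.** Section II includes safety in the aim: "The aim of this study is to evaluate the safety and effectiveness of stent placement in patients with chronic MCA occlusion". Section III.3 (Research Process) allocates patients at random, and only one arm has a procedure: "The control group received aspirin treatment, while the stent group underwent stent placement surgery on the basis of aspirin treatment".

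Section V (Follow up stage) promises that "Regular follow-up will beconducted on all participants to evaluate treatment outcomes". It lists blood flow recovery, reocclusion and neurological recovery, and gives one time: "The follow-up time points is 3 months after surgery". No neurological scale is named, and death is not among the listed outcomes.

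Section IV names the software, the descriptive summaries and an open list of tests: "Inter group comparisons were conducted using methods such as independent sample t-test, Mann Whitney U test, chi square test, or Fisher's exact test". No test is tied to an outcome. Neither section gives an analysis set, a missing-data method, a rule for death or a sensitivity analysis. Section IV reads as complete prose, so the absence does not look like a redaction or a lost table.

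**The concern.** A patient who dies before 3 months normally has no score and no follow-up image. The same holds for one who withdraws or cannot attend, which is plausible in a population enrolled with deficits such as hemiplegia. Run on recorded values with no further rule, the listed tests compare those who survived and were assessed in one arm with those who survived and were assessed in the other.

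Randomisation does not protect that comparison if treatment affects who remains. Procedural deaths can occur only in the stent arm, so loss may differ by arm. Three results are possible:

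- Stent-arm deaths concentrated among patients with a poor prognosis: the remaining stent patients score better with no true benefit.
- Stent-arm deaths unrelated to prognosis: the scores show no difference, and the harm does not appear in the efficacy result.
- Control deaths or selective withdrawal: the bias can run against stenting.

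In a trial that is meant to judge safety as well as effectiveness, the first two matter equally.

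**Working it through.** **Inputs.** The plan has no sample size, event rate, dropout rate, alpha, power or allocation ratio, so there is no figure to reproduce. Everything below is an assumption made to show a range: 1:1 allocation, equal underlying scores in both arms, normal scores with SD 1 (higher is better), losses in the stent arm only, and a two-sided 0.05 test.

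**1. Upper bound: exactly the worst fraction p of the stent arm is lost.** The mean of those left rises by φ(z₁₋ₚ)/(1−p), where φ is the standard normal density.

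- p = 0.02: 0.049 SD
- p = 0.05: 0.109 SD
- p = 0.10: 0.195 SD (0.19 when rounded from the unrounded value, 0.17550/0.90 = 0.19500 less a trace)

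No loss of that size can shift the mean further.

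**2. Milder case: deaths at random within the worse half.** The mean of the worse half is −2φ(0) = −0.798, so the shift is 0.798·p/(1−p). At p = 0.10 this is 0.798 × 0.10/0.90 = 0.089 SD, less than half the upper bound.

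**3. Deaths unrelated to score.** The expected difference among those observed is zero. With deaths ranked worst, the probability that a random stent patient does better than a random control is 0.5(1−p): 0.49, 0.475 and 0.45 at 2%, 5% and 10%. Using observed values only leaves it at 0.50.

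**4. Effect on the test.** Simulation, 3,000 runs per setting, 50 per arm, 10% stent-arm deaths and none in controls:

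| Deaths | Analysis | Favours stent | Favours control |
|---|---|---|---|
| In worse half | Observed-only t-test | 6.4% | 0.8% |
| In worse half | Mann-Whitney, death worst | 0.5% | 5.1% |
| Unrelated to score | Observed-only t-test | 2.7% | 2.8% |
| Unrelated to score | Mann-Whitney, death worst | 0.4% | 14.2% |

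The nominal rate on each side is 2.5%. The results favouring control under worst rank are not false alarms, because the stent arm does have more deaths. With deaths in the worse half, observed-only results favouring stenting at 10% deaths are 5.5% with 30 per arm and 8.7% with 100.

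**5. Reverse direction.** With the 10% of deaths in controls instead (worse half, 50 per arm), the observed-only difference is −0.089 SD. Then 1.0% of trials favour stenting and 6.2% favour control.

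**6. Binary outcome.** Assume 40% good outcome in both arms. If 10% of the stent arm die and all would have done poorly, the observed-only stent rate is 0.40/0.90 = 44.4% against 40.0%; with death counted as failure it is 40.0%. If deaths are unrelated to prognosis, observed-only gives 40.0%, and death as failure gives 0.40 × 0.90 = 36.0%.

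**The case against.** The documents nowhere say that only observed values will be used. The test list is open, and Mann-Whitney, chi-square and Fisher's exact test can all take deaths as worst rank or failure. A scale with a category for death would score those patients. This stands: observed-only analysis is inferred from silence, and the fault is the missing rule, not the tests. It does not close the gap, because no such scale or rule is written and a death category would not cover withdrawals.

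Section V does promise regular follow-up of all participants over February 2022 to February 2023, so contacts other than the 3-month one may be intended. That states who is followed. It does not say how an unassessed patient enters the comparison.

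Worst rank is also not the only legitimate choice. Death as failure in a binary outcome, or mortality reported beside function, would be defensible if fixed in advance.

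A reader might go further and infer that fatal complications will be converted into apparent efficacy. The documents do not support that: nothing in them says that procedural deaths select patients by prognosis, and steps 3 and 5 above give no difference or the opposite sign.

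**Conclusion.** The concern holds as a missing rule. For patients who die, withdraw or go unassessed, the plan leaves their place in the 3-month comparison undefined, and the default is exclusion. Since procedural risk falls on one arm, the result can flatter stenting or hide harm; other patterns of loss can bias against stenting. The direction cannot be settled from the documents.

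Nor can the size. The 0.05, 0.11 and 0.19 SD at assumed losses of 2%, 5% and 10% are upper bounds that need exact removal of the worst tail of one arm and no loss in the other. They should not be read as expected bias. The milder assumption gives about 0.09 SD at 10%. All figures rest on assumed loss rates, normal scores and, for the simulation, assumed arm sizes. The omission itself is certain. The change should be made because it is cheap and has to be settled before the data are seen.

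**What to change.** **In section IV:**

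- Name the neurological scale. Compare all randomised patients as assigned by Mann-Whitney, a test already listed, with death before 3 months given the worst rank or the scale's own death category.
- Count an artery not imaged because of death as flow not recovered. State how death enters the reocclusion comparison, and what reocclusion means for a control artery that was never opened.
- Report deaths and unassessed patients by arm, with reasons.
- Add a sensitivity analysis for patients alive but unassessed, and say how unknown vital status is treated.

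**In section V:**

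- Define the 3-month point from one origin common to both arms, for example randomisation, since controls have no surgery date. The calendar must fit the choice: recruitment opens in May 2021 and treatment in December 2021, so a patient randomised in May would reach 3 months in August, before treatment starts. If the origin is later than randomisation, deaths in between must still count.
- State that patients who stop treatment or miss the visit are still contacted for vital status and function, by a method that suits the chosen scale.

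**Cost:** a short paragraph in each section and a few extra follow-up contacts. The main result becomes a rank-based comparison rather than a mean difference, which is harder to express in units of the scale.
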